**b. Safety Population**

Will include all subjects who receive a PillSense capsule. Safety will be analyzed based on the Safety Population.

### c. Other Populations

Withdrawals: Patients that fulfill inclusion criteria and have signed informed consent but withdrew after inclusion.

## 6.5. Handling of Missing and Incomplete data

All attempts will be made to collect all data per protocol, all practical monitoring and follow up steps will be taken to ensure complete and accurate data collection. Any data point that appears to be erroneous or inexplicable based on clinical judgment will be investigated as a possible

## **STATISTICAL ANALYSIS PLAN**

outlier. If data points are identified as outliers sensitivity analysis may be performed to examine the impact of including or excluding the outliers. Any substantive differences in these analyses will be reported. It is assumed that all missing data will be random.

In mITT population, subjects with missing data will not be counted in the percentage. Number of missing values will be reported.

In Safety population, for AEs with a missing start date, the AE will be considered treatment-emergent unless there is additional information indicating that the AE started prior to study treatment and AEs for which the relationship is missing, will be considered related

### **6.6. Poolability**

The study is performed in only one site, Development Endoscopy Unit, Mayo Clinic, Rochester MN, therefore there are no issues for site heterogeneity.

### **6.7. Data Display Characteristics**

For continuous data, the minimum and the maximum will use the same decimal accuracy as the raw data.

For categorical data, percentages will be reported to one decimal place.

For all one-sided statistical tests, a 0.025 significance level will be used unless otherwise noted. P-values will be reported to 4 decimal places. P-values less than 0.0001 will be displayed as <0.0001 in the tables.

## **7. PATIENT ACCOUNTABILITY**

### **7.1. Patient Disposition**

Patients' flowchart will be drawn describing the excluded patients from the mITT analysis set along with the reason.

### **7.2. Demography:**

Demographic characteristics will be based on mITT analysis set.

Subjects will be summarized with respect to baseline demographics and physical examination (e.g., age, sex, ethnicity, race ,height, weight...etc), These will be summarized by descriptive statistics, including means, medians, standard deviations, minimums, and maximums.

These will be summarized as follows:

- Age (years): summary statistics
- Sex: Male, Female
- Ethnicity: Hispanic or Latino. Not Hispanic or Latino

## **STATISTICAL ANALYSIS PLAN**

- Race: White, Black or African American, American Indian or Alaska Native, Asian, Native Hawaiian, or other Pacific Islander

### **7.3. Medical History:**

Medical History summaries will be based on the complete and mITT analysis set.

The summary tables for medical history and baseline characteristics will be provided detailing the number and percentage of subjects. The following will be summarized for the complete and mITT cohorts:

- Inclusion/exclusion
- Underlying GI disease
- Height(cm) at baseline: summary statistics
- Weight (kg) at baseline: summary statistics
- BMI derived from height and weight: summary statistics
- Blood pressure (mmHg) at baseline: summary statistics
- Heart rate (bpm) at baseline: summary statistics

Reason for those subjects who were withdrawn will be provided separately.

### **7.4. Laboratory parameters**

Laboratory parameters at baseline will be based on mITT analysis set. Subjects will be summarized with respect to Laboratory assessment. These will be summarized by descriptive statistics, including means, medians, standard deviations, minimums and maximums for continuous variables and frequencies and percentages for categorical variables.

These will be summarized as follows:

- Hemoglobin (g/dL) at baseline: summary statistics
- Hematocrit (%) at baseline: summary statistics
- Platelets (x10^3/uL) at baseline: summary statistics
- PT (secs) at baseline: summary statistics
- INR at baseline: summary statistics
- Pregnancy: Yes/No

### **7.5. Medications**

Concomitant medication will be summarized using mITT analysis set.

The summary tables will be provided detailing the number and percentage of each medication. (Ordered alphabetically). A complete list of all concomitant medications will be provided.

### **7.6. PillSense Procedure Information**

Summary tables will be provided detailing the number and percentage of the following:

- Location of procedures (e.g., endoscopy suite (admitted or not) etc.)

## **STATISTICAL ANALYSIS PLAN**

- Total monitoring time
- Device malfunctions (yes/no and type)
- Time between PillSense reading and EGD start time
- PillSense location at time of EGD (stomach or duodenum)
- Other clinically relevant endoscopic findings (yes/no) actual findings will be in listing.
- Additional interventions performed (yes/no) type in listing unless they can be summarized
- Time to PillSense excretion (passage) from the GI tract

### **8. STATISTICAL METHODOLOGY FOR ENDPOINTS**

#### **8.1. Statistical Methods for the Primary Endpoint**

The estimate of sensitivity will be provided together with an exact (Clopper-Pearson) 95% confidence intervals for the true sensitivity. The null and alternative hypotheses for sensitivity are as follows:

$$H_0: p_1 \leq 0.75$$

vs.

$$H_1: p_1 > 0.75$$

where  $p_1$  denotes the true sensitivity. A one-sided, continuity-corrected z-test will be used to test the null hypothesis at the 0.025 level of significance.

The estimate of specificity will be provided together with an exact (Clopper-Pearson) 95% confidence intervals for the true specificity. The null and alternative hypotheses for specificity are as follows:

$$H_0: p_2 \leq 0.60$$

vs.

$$H_1: p_2 > 0.60$$

where  $p_2$  denotes the true specificity. A one-sided, continuity-corrected z-test will be used to test the null hypothesis at the 0.025 level of significance.

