#### **6.2. Sample Size**

Calculations were performed to estimate the minimum total sample size (TSS) required to achieve at least 80% probability of observing a successful outcome for both sensitivity and specificity to detection of Upper GI Bleed (UGIB), each relative to a performance goal. These calculations were performed assuming a prevalence of UGIB (PR) of 30%.

The probability of meeting the sensitivity endpoint is independent from the probability of meeting the specificity endpoint because they are based on different groups of patients. Therefore, the probability of meeting both endpoints (P) was calculated by multiplying the probabilities of meeting the sensitivity and specificity endpoints individually (i.e., by multiplying the statistical powers for the two endpoints).

The power for sensitivity was calculated based on the following specifications:

1. Single-arm study of PillSense
2. Primary endpoint: sensitivity to detection of Upper GI Bleed (UGIB)
3. Comparison to Performance Goal
4. True sensitivity: 0.975
5. Performance Goal: 0.75
6. Z-test with continuity correction
7. One-sided alpha = 0.025
8. Prevalence of UGIB = 30%

The power for specificity was calculated based on the following specifications:

1. Single-arm study of PillSense
2. Primary endpoint: specificity to detection of Upper GI Bleed (UGIB)
3. Comparison to Performance Goal
4. True specificity: 0.80
5. Performance Goal: 0.60
6. Z-test with continuity correction
7. One-sided alpha = 0.025
8. Prevalence of UGIB = 30%

Based on the above specifications, it was determined that 86 subjects (26 with UGIB for sensitivity and 60 without UGIB for specificity) are the minimum TSS that achieves ~80% probability of meeting both the sensitivity and specificity endpoints. With respect to specificity, study enrolment will continue until at least 60 subjects without UGIB are observed. The sample size for specificity

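### The co-primary z-test can fail while the SAP's own Clopper-Pearson interval clears the goal; a one-sided exact binomial test removes the conflict at no cost in patients

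*SAP*

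**What the plan says.** SAP 8.1 sets the null hypotheses at a sensitivity of at most 0.75 and a specificity of at most 0.60. The decision rule is the same for both: "A one-sided, continuity-corrected z-test will be used to test the null hypothesis at the 0.025 level of significance". For estimation it adds an exact interval to each endpoint: "The estimate of sensitivity will be provided together with an exact (Clopper-Pearson) 95% confidence intervals for the true sensitivity", and likewise "The estimate of specificity will be provided together with an exact (Clopper-Pearson) 95% confidence intervals for the true specificity".

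SAP 6.2 powers the study with the same test ("Z-test with continuity correction") and concludes that "86 subjects (26 with UGIB for sensitivity and 60 without UGIB for specificity) are the minimum TSS that achieves ~80% probability" of meeting both endpoints. The number with UGIB is not fixed in the visible text: "With respect to specificity, study enrolment will continue until at least 60 subjects without UGIB are observed". The synopsis gives a range of 86 to 172 patients in total.

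Neither section says whether the z-test uses the null or the observed standard error. Neither says how a disagreement between test and interval would be handled.

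**The concern.** The interval and the test come from different distributions. The Clopper-Pearson lower limit exceeds the goal when the exact upper-tail probability is below 0.025. The z-test uses a continuity-corrected normal approximation. With about 26 cases and a goal of 0.75, that approximation overstates the tail probability, so the z-test can need one more success than the interval does.

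The trial could then report a sensitivity interval lying wholly above 75% and still have to declare the endpoint not met. The unstated standard error adds a second ambiguity, because one result at the planned case count passes or fails according to which form is programmed.

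**Working it through.** **Inputs.** From SAP 6.2 and 8.1: goals 0.75 and 0.60, true values 0.975 and 0.80, one-sided alpha 0.025, prevalence 30%, and 26 subjects with and 60 without UGIB.

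**Formulas.** For x successes in n with goal p0:
- z-test, null standard error: z = (x − n·p0 − 0.5)/√(n·p0·(1 − p0)), reject if z > 1.96
- exact test: reject if P(X ≥ x | n, p0) ≤ 0.025

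**The plan's own figure.**
- Sensitivity, n=26: 24 successes give 4/2.208 = 1.81 (fail) and 25 give 5/2.208 = 2.26 (pass), so the cut-off is 25. Power is P(X ≥ 25 | 26, 0.975) = 0.8629.
- Specificity, n=60: 44 successes give 7.5/3.795 = 1.98 (pass), so the cut-off is 44. Power is P(X ≥ 44 | 60, 0.80) = 0.9228.
- Joint: 0.8629 × 0.9228 = 0.796, which is the stated ~80%.

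With the observed standard error and the same correction, the cut-offs are 24 and 44 and joint power is 0.898. The null form is therefore assumed below.

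**Exact test at the planned split.** The cut-offs are again 25/26 and 44/60, so power is unchanged.

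**Other UGIB counts (goal 0.75).** In each row the z-test fails and the interval clears the goal.

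| Result | z | z-test p | Clopper-Pearson lower limit |
|---|---|---|---|
| 19/20 | 3.5/1.936 = 1.81 | 0.035 | 0.751 |
| 20/21 | 3.75/1.984 = 1.89 | 0.029 | 0.762 |
| 25/27 | 4.25/2.25 = 1.89 | 0.029 | 0.757 |
| 30/33 | 4.75/2.487 = 1.91 | 0.028 | 0.757 |

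Between 20 and 44 cases, the sensitivity cut-offs differ at 20, 21, 27, 33, 38, 39 and 44. They also differ at some counts below and above that range. For specificity they agree at every count from 33 to 79; they differ at, for example, 80 (58 against 57) and 120 (84 against 83).

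**Size.** For n from 1 to 200 the exact cut-off is never above the z cut-off and at most one lower. For n from 1 to 172 the largest true size is 0.0217 (sensitivity) and 0.0237 (specificity) for the z-test, and 0.0249 for both with the exact test. All are below 0.025.

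**How often it bites.** I enumerated the visible enrolment rule: at least 86 subjects, at least 60 without UGIB, cap 172. At 30% prevalence:
- chance of a UGIB count where the sensitivity cut-offs differ: 20.4%
- sensitivity power: 0.865 (z) against 0.905 (exact), so the chance of a failed test beside a clearing interval is 0.905 − 0.865 = 4.0%
- of those 4.0 points, about 2.8 come from counts of 20 and 21, and 0.7 from 27

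Joint power, z-test against exact. Prevalences other than 30% are assumptions, as is the rule in the last column.

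| Prevalence | Visible rule | Visible rule plus at least 26 UGIB cases |
|---|---|---|
| 20% | 42.4% vs 61.9% | 85.0% vs 85.2% |
| 25% | 66.2% vs 75.7% | 83.4% vs 83.8% |
| 30% | 79.7% vs 83.5% | 84.1% vs 85.0% |
| 35% | 87.0% vs 88.3% | not needed here |
| 40% | 90.5% vs 91.0% | not needed here |

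**The unstated standard error.** At 24/26 the null form gives p=0.035 (fail). The observed form gives z = (4/26)/√(0.923 × 0.077/26) = 2.94, p=0.0016 (pass). The exact p is 0.0258 and the Clopper-Pearson lower limit is 0.749, so the exact test fails it. A cut-off of 24 at n=26 has true size 0.0258, above 0.025.

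**The case against.** The SAP prespecifies a valid test, powers the study with it, and offers the interval only for estimation. It never makes the interval a decision rule, so there is no formal contradiction. At the planned 26 and 60 the two rules coincide, and any loss falls on the sponsor. That is right, and it limits the weight of the point.

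The probabilities also depend on text that cannot be seen. Section 6.3 is redacted, the abbreviation list includes conditional power, and the enrolment sentence is limited to specificity, so a separate provision for UGIB cases may exist. If at least 26 cases were secured, the gain would be under half a point at 20% and 25% prevalence and just under one point at 30%. If exactly 26 or 52 cases were fixed, the sensitivity gain would be zero. The large gaps at low prevalence mainly reflect too few bleeds, and the exact test does not bring those rows to 80% either. They should not be read as the value of changing the test.

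Finally, the protocol text is written in the past tense, so the study may already be complete. Changing the test would then lower the bar at some counts after the fact.

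The inconsistency and the unstated standard error survive all of this. The exact test is never stricter than the null-form z-test, holds alpha, and agrees with the interval already promised.

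**Conclusion.** The point holds as something to consider. Under the null standard error the z-test is valid but conservative, and at some UGIB counts, 27 among them, it can fail while the reported interval excludes the goal. The practical effect is on sensitivity.

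On the visible enrolment rule at 30% prevalence and true sensitivity 0.975, it costs 4.0 points of sensitivity power and about 3.8 points of joint power (83.5 − 79.7). The joint loss could be 0.9 points (85.0 − 84.1) or less if the redacted section protects the UGIB count. The plan delivers its stated ~80% either way.

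The conclusion rests on the null standard error, which the SAP does not state but which its own power figure supports. Under the observed form the size would exceed 0.025 at n=26, and the conflict there would run the other way.

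**What to change.** Before PillSense results are compared with EGD, replace the z-test in SAP 8.1, and line 6 of each specification list in SAP 6.2, with the one-sided exact binomial test at 0.025 for both endpoints. State the equivalent rule beside it: an endpoint is met if the lower limit of its two-sided 95% Clopper-Pearson interval exceeds the goal. The ~80% figure can stay, because nothing changes at 26 and 60.

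If results are already known, do not switch. Keep the z-test as the decision rule, state its standard error, and report the exact p-value beside it as supportive.

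The cost is SAP wording and no extra patients. The success cut-off falls by one at some counts, so the change must be fixed before results are seen. Alpha stays at or below 0.025 provided the sample size is not chosen from PillSense results. Any conditional-power rule in the redacted section 6.3 would need its own check.

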#### **8.2. Statistical Methods for the Secondary Efficacy Endpoints**

Secondary analysis will be performed based on mITT population. Secondary endpoints are for informational purposes only.

- Observed value along with exact (Clopper Pearson) 95% CI of Positive Predictive Value (PPV)
- Observed value along with exact (Clopper Pearson) 95% CI of Negative Predictive Value (NPV)
- Observed value along with exact (Clopper Pearson) 95% CI of Positive Likelihood Ratio (PLR)
- Observed value along with exact (Clopper Pearson) 95% CI of Negative likelihood Ratio (NLR)
- Observed value along with exact (Clopper Pearson) 95% CI of Accuracy.

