### **5.3. Exploratory Analysis**

The exploratory analysis are as follows:

- Positive likelihood ratio (PLR) of the PillSense System
- Negative likelihood ratio(NLR) of the PillSense System
- Accuracy of PillSense capsule

These are defined as follows:

PLR: Probability (odds) of having “Blood detected” in a patient with bleeding.

Sensitivity

---

1-Specificity

NLR: Probability (odds) of having “Blood detected” in patients with no bleeding/

1-Sensitivity

---

Specificity

Accuracy: Correct classification rate is the proportion of observations for which the test result and actual response agree.

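### Clopper-Pearson intervals are specified for the positive and negative likelihood ratios, which are not binomial proportions, so the planned intervals cannot be validly computed

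*SAP*

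**What the plan says.** SAP 8.2 lists five measures and gives all of them the same interval. For the likelihood ratios the entries are "Observed value along with exact (Clopper Pearson) 95% CI of Positive Likelihood Ratio (PLR" and "Observed value along with exact (Clopper Pearson) 95% CI of Negative likelihood Ratio (NLR". The other three are PPV, NPV and accuracy. The readable text names no other interval method for the likelihood ratios.

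SAP 5.3 defines the two ratios twice, in words and by formula:

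- **Positive ratio (PLR).** In words: "PLR: Probability (odds) of having “Blood detected” in a patient with bleeding". The formula printed beneath is sensitivity divided by 1 − specificity.
- **Negative ratio (NLR).** In words: "NLR: Probability (odds) of having “Blood detected” in patients with no bleeding". The formula printed beneath is 1 − sensitivity divided by specificity.

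The two sections also differ on status. SAP 5.3 lists both ratios, and accuracy, as exploratory. SAP 8.2 places them under the secondary efficacy heading, with the remark "Secondary endpoints are for informational purposes only".

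**The concern.** A Clopper-Pearson interval inverts the binomial distribution for a single proportion x/n. Neither likelihood ratio has such an x and n. Each combines a proportion among patients with bleeding and a proportion among patients without, and SAP 6.2 itself says of sensitivity and specificity that "they are based on different groups of patients". The instruction is therefore wrong as written; it is not a choice between acceptable methods.

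The verbal definitions open a second route to error. Read literally, the PLR sentence describes sensitivity and the NLR sentence describes 1 − specificity. An analyst who follows the words obtains proportions that Clopper-Pearson software accepts without complaint, but they are the wrong quantities, and each reflects sampling error from only one of the two groups. An analyst who follows the formulas cannot run the named method and must choose another after seeing the data.

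**Working it through.** **Inputs.** From SAP 6.2: "True sensitivity: 0.975", true specificity 0.80, performance goals 0.75 and 0.60, and 86 subjects split into 26 with bleeding and 60 without. The formulas are those in SAP 5.3. The SAP gives no figure for either ratio, so the counts used below (25/26 detected, 48/60 correctly negative, hence 1 false negative and 12 false positives) are assumed, chosen near the planning values.

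**The plan's own figure.** The joint power of about 80% reproduces. With the continuity-corrected z-test at one-sided 0.025, success needs at least 25/26 (power 0.863) and at least 44/60 (power 0.923); 0.863 × 0.923 = 0.796. This confirms the planning inputs and has no further bearing on the point.

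**Can a Clopper-Pearson interval contain the ratios?**

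| Scenario | PLR = Se/(1 − Sp) | NLR = (1 − Se)/Sp |
|---|---|---|
| Planning values | 0.975/0.20 = 4.875 | 0.025/0.80 = 0.031 |
| Both performance goals | 0.75/0.40 = 1.875 | 0.25/0.60 = 0.417 |

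The limits lie within [0, 1], so PLR falls outside in both rows. NLR happens to be below 1 but still has no single x/n behind it. PPV, NPV and accuracy are single proportions, so the method can be used for them.

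**What following the words would give.** Clopper-Pearson on 25/26 is 0.80 to 1.00 (this is sensitivity). On 12/60 it is 0.11 to 0.32 (this is 1 − specificity).

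**Intervals for the right quantities, log method.**

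- PLR = (25/26)/(12/60) = 4.81. SE(ln PLR) = √(1/25 − 1/26 + 1/12 − 1/60) = 0.261. 95% CI = 4.81 × exp(±1.96 × 0.261) = 2.88 to 8.02.
- NLR = (1/26)/(48/60) = 0.048. SE(ln NLR) = √(1/1 − 1/26 + 1/48 − 1/60) = 0.983. 95% CI = 0.048 × exp(±1.96 × 0.983) = 0.007 to 0.330.

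**Same counts, Koopman score method.** This collects every ratio θ not rejected by the score test of p1 = θ·p2 for two independent binomials. PLR: 2.99 to 8.16. NLR: 0.009 to 0.238.

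**No false negatives.** At true sensitivity 0.975 the chance that all 26 patients with bleeding are detected is 0.975^26 = 0.518. NLR is then 0, and the plain log method fails because 1/FN is undefined. With 0/26 and 48/60:

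- The Koopman interval is 0 to 0.161.
- The log method with 0.5 added to each cell gives 0.023 (0.0015 to 0.364).

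The two upper limits differ by a factor of 0.364/0.161 = 2.3.

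**The case against.** The strongest counter-argument is about consequence. Both ratios are exploratory in SAP 5.3, SAP 8.2 calls its endpoints informational, and no hypothesis test or decision rests on them. The co-primary tests and their Clopper-Pearson intervals, the alpha level and the sample size are unaffected. This stands: it limits the importance of the point but does not make an undefined interval usable.

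Other objections stand in part:

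- **The formulas in 5.3 are clear.** A careful analyst would probably follow them, so estimating the wrong quantity is a risk and not a certainty. The wording also says odds as well as probability, and the NLR sentence ends in a stray slash, so it may be incomplete. Even so, the named method cannot be run on the formulas, and the replacement would be chosen after the data are seen.
- **A score interval is not the only remedy for a zero cell.** A 0.5 correction also yields limits. The two answers differ by more than a factor of two at the upper end, which is a reason to fix the choice in advance.
- **Clopper-Pearson limits can be combined.** Taking 97.5% limits for sensitivity and specificity separately gives conservative bounds for 25/26 and 48/60: PLR 2.28 to 10.21 and NLR 0.0005 to 0.336. That is a different procedure, and the SAP does not describe it.
- **The 52% assumes exactly 26 patients with bleeding.** Enrolment runs until 60 without bleeding are observed, so the number with bleeding will vary. At the same sensitivity the probability is 0.975^20 = 0.60 with 20 such patients and 0.975^40 = 0.36 with 40. A zero cell remains a realistic outcome across that range.

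**Conclusion.** The concern holds. SAP 8.2 prescribes, for two listed accuracy measures, an interval that does not exist for them, and the verbal definitions in SAP 5.3 contradict the formulas printed with them. The mismatch rests only on the SAP's formulas and on its statement that the two groups are separate; it needs no assumption about results. The numerical intervals are illustrations from assumed counts, and the chance of a zero cell depends on the assumed sensitivity and on the number of patients with bleeding.

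The point should be corrected, but it does not threaten the trial's main conclusions. It affects the reported uncertainty of two descriptive measures and nothing in the co-primary analysis.

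**What to change.** 1. In SAP 8.2, replace Clopper-Pearson for PLR and NLR with a 95% score interval for a ratio of two independent proportions, naming either Koopman or Miettinen-Nurminen. It also handles a zero false-negative count. If the sponsor prefers the log method, state the zero-cell rule alongside it.
2. Keep Clopper-Pearson for PPV, NPV and accuracy.
3. In SAP 5.3, correct the words to match the formulas. PLR is P(blood detected | bleeding) divided by P(blood detected | no bleeding). NLR is P(no blood detected | bleeding) divided by P(no blood detected | no bleeding).
4. In SAP 8.2, label PLR and NLR as exploratory, as 5.3 does. Accuracy has the same mismatch and can be relabelled in the same edit.

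The cost is a few lines of SAP text and a standard software option. No additional patients or data are needed, and the primary analysis does not change.
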